The study site is Kisinga Subcounty, comprising 25 villages (LC1). *SASA! Together* community programming is currently underway in 23 of these villages. From these 23, one will be purposively selected for questionnaire piloting based on logistical considerations. The other 22 will form the sampling frame for the community members survey. We will employ a multi-stage sampling strategy, with village as the primary sampling unit (PSU).

Sampling of villages

The original plan was to conduct the survey in all remaining 22 villages. However, this plan was modified due to seven of the villages being relatively inaccessible (3-4 hours walk from the next nearest village). For logistical purposes therefore, we decided to drop four of the less accessible villages from the sampling frame, while still retaining three of them in order to be able to estimate intervention reach to these more remote locations. Among the remaining 18 villages, stratified random sampling (stratifying by urban/rural and population size) will be used to select half of these (9) to form the basis of the sample of female community members. The other half (9) will form the basis of the male sample. This designation of male/female villages will remain the same for both survey timepoints to maintain comparability between survey rounds.

Sampling of households within villages

Allowing for failure to contact respondents, refusals to participate, and households without any eligible members, we will oversample households by 10% in order to achieve our target sample size of 650 respondents at baseline and 980 respondents at endline.

Within each village, 40 households will be sampled at baseline and 60 at endline. Different households will be sampled at each time-point, with the sampling strategy explicitly designed to avoid resampling the same households in multiple survey rounds. This both minimises respondent burden and eliminates the risks (discussed below) that might arise if two different members of the same household were selected to participate in the study in separate survey rounds.

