Sample size has been determined based on a combination of pragmatic and theoretical considerations. As discussed, since the Radio Booster is in the early stages of development, smaller scale process-oriented research is deemed necessary before investment in a larger impact evaluation is undertaken. We thus focus here on study precision and power in relation to Objective 1, estimating Radio Booster listenership. After determining a feasible sample size based on logistical and resource constraints, we estimated the precision with which we would be able to estimate Radio Booster listenership overall, among respondents with access to a radio, and separately by sex (Table 1). (NB: These calculations were done prior to the increase in planned endline sample size, and therefore assume a sample size of 650 respondents at each time-point.) We also estimated study power to detect statistically significant differences (significance level 10%) in listenership between those participating and not participating in *SASA! Together* community activities, and between women and men (Table 2). We present precision and power estimates for a range of scenarios, in which we vary assumed values for listenership prevalence, prevalence differences between sub-groups (where applicable), and inter-village variation in listenership (as represented by the design effect [DE]). Study precision and power are high in most of these scenarios. We expect that the DE will be close to 1 as the study site is small and radio station coverage is high throughout the site.

Inclusion and exclusion criteria

Individuals from selected households will be eligible for inclusion in the survey if they are aged 18 years or above and are proficient in the Lukonzo language. Eligibility will also depend on sex: in villages chosen to form the basis of the female sample, only women will be eligible for inclusion; while in villages chosen to form the basis of the male sample, only men will be eligible for inclusion.

Among randomly selected participants, efforts will be made to include those with intellectual or other disabilities where possible. However, the survey will not be administered to individuals who do not have the capacity to understand the questions being asked, or in cases where privacy would be compromised by the involvement of another household member to help complete the questionnaire.

Informed consent and survey procedure

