Descriptive data will be produced at each time point for all of the indicators relating to the Radio Booster's reach. In addition to producing overall proportions, we will disaggregate the data by sex, age and other key demographic characteristics. Chi-squared tests of association and regression analysis with cluster robust standard errors will be used to assess differences in the Radio Booster's reach between these subgroups.

Objective 2a:

Chi-squared tests of association and/or T-tests will be used to assess the association between listening to the booster and attendance at SASA! Together activities.

Objective 4:

Differences between baseline and endline community-level attitudes towards IPV and intimate relationships, quality of intimate relationships, and activism to respond to/prevent IPV, will be assessed with the use of appropriate statistical tests. A difference-in-difference analysis (or similar)

will be conducted to assess whether changes differ between radio booster listeners and non-listeners, after accounting for other *SASA! Together* community exposure and key demographics.

If there is sufficient variation in frequency with which respondents listen to the Radio Booster, we will conduct a dose-response analysis to assess whether greater exposure to the Booster is associated with better outcomes at endline. This will comprise logistic regression (for binary outcomes) or linear regression (for continuous outcomes), with independent variables comprising Radio Booster exposure level, village-level baseline measure of the outcome, exposure to *SASA! Together* community activities, and key demographics.

Qualitative

The qualitative component of the evaluation will comprise in-depth interviews (IDIs), key informant interviews (KIIs), focus group discussions (FGDs) and recorded listener groups. IDIs, KIIs and FGDs will be longitudinal in design, interviewing the same cohort of people at more than one time-point.

In-depth interviews

IDIs will be conducted with community members in Kisinga subcounty who have listened to the Radio Booster ("listeners").

Each listener will be interviewed at two time-points – approximately 19 weeks after the Radio Booster begins airing, and shortly after Radio programming finishes (approximately 37 weeks) – allowing us to explore how experiences of and engagement with the Radio Booster change over time.

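### Sex comparisons are 9 villages against 9, but the by-sex precision and power in Tables 1 and 2 make no allowance for so few villages, and the expected design effect near 1 is weakly supported

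*Protocol*

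**What the plan says.** Under Sampling frame, the design is multi-stage "with village as the primary sampling unit (PSU"). Under Sampling of villages, stratified random sampling by urban/rural status and population size "will be used to select half of these (9) to form the basis of the sample of female community members"; then "The other half (9) will form the basis of the male sample". The split does not change: "This designation of male/female villages will remain the same for both survey timepoints". Under Sampling of households within villages, "Within each village, 40 households will be sampled at baseline and 60 at endline".

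Study precision/power gives no ICC. It represents variation between villages by DE values of 1, 1.5 and 2, tabulated in every row of Tables 1 and 2, and calls precision and power high in most scenarios. It then says "We expect that the DE will be close to 1 as the study site is small" and that radio coverage is high across the site. It states openly that the tables predate the larger endline sample.

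Sampling of villages also reports "seven of the villages being relatively inaccessible (3-4 hours walk from the next nearest village"). Four of these seven were dropped. Three were kept so that reach in remote places could be estimated.

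Under Statistical analysis, Objective 1, "Chi-squared tests of association and regression analysis with cluster robust standard errors will be used" for subgroup differences in reach. The same section promises that analyses will allow for clustering and leaves detail to a later analysis plan.

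**The concern.** Because no village contributes both sexes, sex is a village-level factor. A difference in listenership between women and men is a difference between two sets of nine villages. It carries the full design effect and has 9 + 9 − 2 = 16 degrees of freedom, however many people are interviewed. A single-sex estimate has 9 − 1 = 8.

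Sex is the first subgroup named under Objective 1 and has its own rows in both tables. If those rows ignore the number of villages, the stated intervals are too narrow and the stated power too high. If the DE is also larger than expected, the shortfall grows, and the extra endline interviews offset it only in part. A sex gap in reach could also reflect which villages fell in which half. The Strengths and limitations section does not mention this.

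**Working it through.** **Inputs.** 325 per sex in the tables and 490 per sex at endline (Sampling strategy and sample size; Tables 1 and 2). Nine villages per sex (Sampling of villages). Two-sided alpha 0.10 for power and 95% confidence for precision (Tables 1 and 2). Respondents per village: 325/9 = 36.1 and 490/9 = 54.4. The ICC is not given, so 0 to 0.05 is an assumed range.

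**Step 1: reproduce the plan.**
- Half-width = 1.96 × √(0.25 × DE/325), which gives 5.44, 6.66 and 7.69 points at DE 1, 1.5 and 2 (stated 5.44, 6.67, 7.70).
- Power for 50% v 60%, from the two-proportion normal approximation with n = 325/DE per group, is 82.2, 67.4 and 56.7% (stated 82.2, 67.2, 56.6%). All four by-sex rows agree within 0.2 points.
- The DE is therefore the only allowance for clustering in these rows.

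**Step 2: same DE, village-level degrees of freedom.** The half-width uses t(0.975, 8) = 2.306 in place of 1.96, a factor of 1.18. Power uses the noncentral t with 16 df, critical value 1.746, and noncentrality 0.10/√[(0.5×0.5 + 0.6×0.4) × DE/325], which is 2.575, 2.103 and 1.821.

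| By sex, 325 each | DE 1 | DE 1.5 | DE 2 |
|---|---|---|---|
| Half-width at 50%, stated | 5.44 | 6.67 | 7.70 |
| Half-width at 50%, t with 8 df | 6.40 | 7.83 | 9.04 |
| Power 50 v 60%, stated | 82.2 | 67.2 | 56.6 |
| Power 50 v 60%, t with 16 df | 79.4 | 64.4 | 54.0 |
| Power 60 v 70%, stated | 84.9 | 70.4 | 59.6 |
| Power 60 v 70%, t with 16 df | 82.3 | 67.6 | 56.9 |

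For 20-point gaps the loss is under 1 point (40% v 60% at DE 2: 97.7% becomes 96.9%).

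**Step 3: what the DE values mean.** ICC = (DE − 1)/(m − 1).
- At m = 36.1, DE 1.5 is 0.5/35.1 = 0.014 and DE 2 is 1/35.1 = 0.0285.
- An ICC of 0.0285 at 50% prevalence is a between-village SD of √(0.0285 × 0.25) = 0.084, about 8 points.
- At endline the same ICC gives DE = 1 + 53.4 × 0.0285 = 2.52.

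| 50 v 60%, t with 16 df | 325 per sex: DE | Power | 490 per sex: DE | Power |
|---|---|---|---|---|
| ICC 0 | 1.00 | 79.4% | 1.00 | 91.6% |
| ICC 0.01 | 1.35 | 68.3% | 1.53 | 78.8% |
| ICC 0.0285 | 2.00 | 53.9% | 2.52 | 60.3% |
| ICC 0.05 | 2.76 | 43.8% | 3.67 | 47.5% |

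**Step 4: size of the test by sex.** Simulation under no sex difference: beta-binomial, 9 v 9 villages, 36 per village, prevalence 50%, 20,000 runs, nominal 10%.
- Plain chi-squared rejects 19% at DE 1.5 and 25% at DE 2.
- Cluster-robust logistic regression with the G/(G − 1) factor and z rejects about 13%.
- Cluster-robust linear regression with t on 17 df rejects about 11%.

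**The case against.** The strongest reply is that the protocol does not depend on a DE of 1. It shows DE 1.5 and 2 in every row, and a reader can see power for 10-point gaps fall below 60%. This stands. At matched DE the t quantile costs only about 3 points of power, and the sample size was set by feasibility in a process study, so restating the tables would not change it. It also stands that high radio coverage is a relevant reason for low variation between villages, that only three of the 18 surveyed villages are remote, and that single-sex villages are a deliberate safety measure.

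Some stronger readings are tempting but not supported:
- A reader might set the ICC-based power of 44 to 68% against the stated 82.2%. That compares different cells, because 82.2% is the DE 1 figure. The plan's own method at ICC 0.01 and 0.05 gives 71.3% and about 46%.
- A reader might infer that the planned analysis is uncorrected for few clusters, or unadjusted for village characteristics. The protocol says neither. It promises to allow for clustering and defers detail.
- A reader might infer an invalid remote-versus-other test, or a false sex gap of a given size caused by remote villages. The protocol specifies no such test and gives no figure for remote listenership.
- A reader might want the participation rows restated too. If participation varies within villages, applying the full DE there is merely conservative.

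**Conclusion.** The point holds in limited form. Sex is confounded with village by design, and the by-sex rows of both tables omit the consequence. At the plan's own DE values, single-sex intervals should be about 18% wider and power for a 10-point gap about 3 points lower; conclusions about 20-point gaps are unchanged.

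The larger uncertainty is the DE itself. The expectation that it will be close to 1 rests on site size and coverage. Yet remote villages were kept in order to estimate reach there, and a modest ICC of about 0.028 already doubles the variance at baseline. At endline that ICC exceeds the tabulated range, although power is still higher than at baseline (60.3% v 53.9%).

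The t-based figures assume equal-sized villages and a common ICC. The ICC range is an assumption, not taken from the protocol.

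**What to change.** 1. Restate the by-sex rows of Tables 1 and 2 with t quantiles (8 df for one sex, 16 for the comparison), over an assumed ICC range such as 0.01 to 0.05, for both 325 and 490 per sex. Drop or qualify the expectation that the DE will be close to 1.
2. In sex comparisons, adjust for the village allocation strata (urban/rural, population size) and for remoteness. Remoteness was not a stratification factor, and three remote villages cannot divide evenly between the sexes. Each village-level covariate uses one of the 16 df, so keep the coding simple.
3. For sex, specify a cluster-adjusted test with village-level degrees of freedom in place of a plain chi-squared test.
4. Add to Strengths and limitations that sex gaps are between-village comparisons and cannot be separated from village differences.

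The cost is two recalculated tables and a few sentences, with somewhat wider intervals and slightly lower stated power. Fieldwork and the single-sex village design stay as they are.

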Survey responses will be entered directly on to a tablet computer using the ODK software with automatic encryption. The software includes in-built filters and checks to minimize the level of missing or erroneous data. The data recorded on the tablet computer will be uploaded daily to a password-protected Sharepoint study database (administered by LSHTM) and further checked for missing and/or erroneous data. Any data queries will be sent to the field supervisors to be resolved with the researchers conducting the interviews. The research firm, Research World International, will make weekly data backups on to a password-protected secure drive. Data backups will also be made weekly by LSHTM. No personal identifying information will be collected - all electronic data are anonymous, with each respondent allocated a unique study identifier.

Consent forms will be stored securely in locked filing cabinets in secure locations arranged by Research World International. These will be transferred to locked filing cabinets in Raising Voices' offices upon completion of each survey round.

Data and paper records will be stored for a minimum of 10 years after study completion.

At the conclusion of our main study analyses, anonymised data from the quantitative survey will be deposited in the LSHTM Data Compass digital repository for research outputs. Any variables that present risk of reidentification will be removed before the data are deposited, as will any variables that could be stigmatising to communities involved in the research. Due to the sensitive nature of the data, it will be made available under restricted access terms (i.e. users will need to apply for access, meet access conditions including applying for ethical approval, and sign an agreement on use). Requests for data use will be reviewed on a case-by-case basis by LSHTM and Raising Voices before decisions are made as to whether or not to grant access. The study protocol and community-member survey will be openly available to all on LSHTM Data Compass.

Statistical analysis

Data will be analysed in Stata SE. Analyses will take account of the clustered nature of the data. A detailed analysis plan will be drawn up prior to conducting the final analysis, but key elements are outlined below.

Objective 1a, b, c, f, g:

Descriptive data will be produced at each time point for all of the indicators relating to the Radio Booster's reach. In addition to producing overall proportions, we will disaggregate the data by sex, age and other key demographic characteristics. Chi-squared tests of association and regression analysis with cluster robust standard errors will be used to assess differences in the Radio Booster's reach between these subgroups.

Objective 2a:

Chi-squared tests of association and/or T-tests will be used to assess the association between listening to the booster and attendance at SASA! Together activities.

Objective 4:

Differences between baseline and endline community-level attitudes towards IPV and intimate relationships, quality of intimate relationships, and activism to respond to/prevent IPV, will be assessed with the use of appropriate statistical tests. A difference-in-difference analysis (or similar)

will be conducted to assess whether changes differ between radio booster listeners and non-listeners, after accounting for other *SASA! Together* community exposure and key demographics.

If there is sufficient variation in frequency with which respondents listen to the Radio Booster, we will conduct a dose-response analysis to assess whether greater exposure to the Booster is associated with better outcomes at endline. This will comprise logistic regression (for binary outcomes) or linear regression (for continuous outcomes), with independent variables comprising Radio Booster exposure level, village-level baseline measure of the outcome, exposure to *SASA! Together* community activities, and key demographics.

Qualitative

The qualitative component of the evaluation will comprise in-depth interviews (IDIs), key informant interviews (KIIs), focus group discussions (FGDs) and recorded listener groups. IDIs, KIIs and FGDs will be longitudinal in design, interviewing the same cohort of people at more than one time-point.

In-depth interviews

IDIs will be conducted with community members in Kisinga subcounty who have listened to the Radio Booster ("listeners").

Each listener will be interviewed at two time-points – approximately 19 weeks after the Radio Booster begins airing, and shortly after Radio programming finishes (approximately 37 weeks) – allowing us to explore how experiences of and engagement with the Radio Booster change over time.

At the first time-point, we will conduct 24 IDIs with listeners (12 men and 12 women). At the second time-point, we will conduct 20 IDIs with listeners (10 men and 10 women). Listeners will be recruited from *SASA! Together* listener groups and will be purposively selected to represent different levels of listenership. Interviewers will conduct IDIs at the first time-point remotely, by telephone, rather than face-to-face (due to an Ebola outbreak affecting Western and Central Uganda, as detailed in the Protocol amendment section below). At the second time-point, interviews may be conducted by telephone or in person.

Potential participants will be identified by Community Activists operating in Kisinga subcounty. Community Activists will, with their consent, take the phone number of potential participants. These phone numbers will be shared with UGANET, who will share them with Research World International for the purpose of recruiting participants. Interviewers will telephone potential participants to explain the study and request their consent to participate in an IDI. If the potential participant chooses to participate, the interviewer will either conduct the IDI then or will arrange a future time and date to conduct the IDI. The interviewer will conduct the consenting process directly before conducting the IDI.

IDIs with community members will explore motivations/facilitators for listening to the Booster (Objective 1d) and barriers to listening (Objective 1e); community members' perceptions of the Booster's influence (Objectives 3a-e); the extent to which the Booster increases engagement with *SASA! Together* activities (Objective 2a) and reinforces *SASA! Together* messaging (Objective 2b); and safety issues around listening/radio content (Objective 2d).

Key informant interviews

KIIs will be held with Community Activists and staff from UGANET/ Raising Voices/ PVI. Key informants will be selected purposively to include those with extensive involvement and varied roles in intervention implementation and/or design.

Each Community Activist will be interviewed at two time-points – approximately 19 weeks after the Radio Booster begins airing, and shortly after Radio programming finishes (approximately 37 weeks). We will conduct 15 IDIs with Community Activists at the first time-point and 12 IDIs with Community Activists at the second time-point.

Community Activists who have extensive experience in *SASA! Together* programming (“model Community Activists”) will be identified by UGANET, and recruited into the study by researchers from Research World International. As there are only 2 model Community Activists operating in Kisinga subcounty, we will recruit model Community Activists from across Kasese district.

Interviewers will conduct KIIs with Community Activists at the first time-point remotely, by telephone, rather than face-to-face. At the second time-point, interviews may be conducted by telephone or in person.

During the process of identifying participants, members of staff from UGANET will obtain potential participants’ phone numbers. These phone numbers will be shared with Research World International for the recruitment process. Interviewers will telephone potential participants to explain the study and request their consent to participate in an IDI. If the potential participant chooses to participate, the interviewer will either conduct the IDI then or will arrange a future time and date to conduct the IDI. The interviewer will conduct the consenting process directly before conducting the IDI.

6 KIIs with UGANET/ Raising Voices/ PVI staff will take place at one time-point only (approximately 37 weeks), in order to gain overall experiences of and reflections on Radio Booster implementation and its role within broader *SASA! Together* programming.

To mitigate the power dynamics which can exist between staff members in all research interactions, we will purposively select KII participants jointly across the full team of UGANET, Raising Voices and PVI staff. Staff will be selected based on their role in the study but their participation will be voluntary. Selection and recruitment of staff will be led by LSHTM researchers with input from staff at UGANET, Raising Voices and PVI. LSHTM staff will conduct all KIIs with staff members as LSHTM does not employ staff from any of these organisations. LSHTM has an equal partnership with Raising Voices, rather than an employer-employee relationship. UGANET and PVI are sub-contracted to work for Raising Voices, but are not employed by them.

KIIs with UGANET/ Raising Voices/ PVI staff and Community Activists will explore staff and community activists’ experiences of implementing the radio drama intervention (Objective 1h); the extent to which the Booster increases engagement with *SASA! Together* community activities (Objective 2a); the role of ‘listener groups’ in promoting critical thinking about Radio Booster content/facilitating links with *SASA! Together* ideas (Objective 2c); and ethical issues arising from implementation (Objective 2d).

Focus-group discussions

FGDs will take place with

- 2 ‘listener groups’ (1 female group, 1 male group)
- 2 groups of *SASA! Together* Community Activists (1 female group, 1 male group)

- 1 group of community leaders (cultural/religious/local government)

Each 'listener group' and group of Community Activists will take part in two FGDs, at approximately 6 weeks and 37 weeks after the Radio Booster begins airing. Repeated focus groups will allow assessment of how reception of and responses to the Booster change over time. The FGD with community leaders will take place at one time point (approximately 37 weeks) to allow reflection on the entire period of Radio Booster implementation.

Listener groups will be identified and selected with the help of *SASA! Together* Community Activists who have been involved in setting up and facilitating these groups. Activists to be interviewed will be purposively selected by UGANET to represent a range of ages, duration of involvement with the intervention and community characteristics. UGANET will also help identify community leaders (cultural, religious and local government) with whom they have had involvement during implementation of *SASA! Together* programming. Recruitment of all of these individuals into relevant focus groups will be conducted by Research World International in order to maintain the independence of the research process.

FGDs with listener groups will explore the acceptability and enjoyment of the Radio Booster content (Objectives 1d, 1e, 3a), the role of listener groups in promoting critical thinking about radio booster content/facilitating links with *SASA! Together* ideas (Objective 2c), and perceptions of the Radio Booster's influence within the community (Objectives 3c-3e).

FGDs with Community Activists will explore the same themes as those explored in the KIIs with programme implementers and CAs.

The FGD with community leaders will explore the acceptability of the Radio Booster content to religious, cultural and local government institutions, as well as its reception among and influence on the local community and institutional practices (Objective 3f).

Listener group recordings

We will conduct up to 8 audio recordings of listener group meetings held between week 19 and week 33 of the intervention. Each listener group will engage in no more than 6 recordings. During the listener group, the facilitator will play a radio episode and then facilitate a discussion about its content. We will record the discussion of the radio drama episode, including anything said by both facilitators and participants. Each discussion is expected to last no more than 40 minutes, including the consenting procedure.

Informed consent and interview procedure

For in-person data collection

As with the community-member survey, individual written informed consent will be obtained for all individuals participating in in-person IDIs, KIIs, FGDs and recorded listener groups. An information sheet about the study will be read aloud to all participants by data collection staff. In cases where the participant is unable to read or write, an impartial witness must be present during the consent procedures and must print and sign their name, with the date, on the consent form on behalf of the potential participant. Participants who are unable to write will use thumbprints in place of signatures to sign the consent form.

In the case of recorded listener groups, both listener group participants and facilitators will be considered study participants, and as such will all be required to give consent to be recorded.

IDIs and KIIs will be conducted in a private place of the respondents choosing, and conducted by interviewers that are the same sex as the respondent. Locations of FGDs will be selected by the field coordinator with the help of Community Activists, to ensure privacy and the safety of participants. As with the quantitative survey, the IDIs, KIIs and FGDs will be conducted in accordance with international guidelines for the collection of data on violence against women(19).

For remote data collection (by telephone)

Individual verbal informed consent will be obtained for all individuals participating in IDIs and KIIs conducted remotely by telephone. An information sheet about the study will be read aloud to all participants by the interviewer over the phone. The interviewer will discuss the information sheet with the participant and seek verbal consent for their participation. If the participant gives verbal consent, the interviewer will attest to this by writing the name of the participant on a paper copy of the consent form and signing and dating their own name on the same form.

Qualitative data management and analysis

All IDIs, KIIs, FGDs and recorded listener groups will be audio recorded with the participants' consent. Audio recordings and hand-written notes are transcribed verbatim and translated from Lukonzo into English. A sample of the transcripts are checked for quality of transcription and translation. Data will be uploaded onto NVivo and analysed following a qualitative thematic analysis approach where notes will be disaggregated by gender and age, and analysed thematically in order to answer the objectives of the study.

Personal identifying information will be collected from all IDI, KII and FGD participants due to the longitudinal nature of this research and the need to contact participants to arrange second and third phases of data collection. Only staff from Research World International, Raising Voices, LSHTM and the local Research Ethics Committee and Uganda National Council for Science and Technology (UNCST) will have access to private information that identifies participants by name. Personal identifying information of staff members from Raising Voices, UGANET or PVI who participate in KIIs will not be shared with Raising Voices or other partners who they work with directly. One list containing personal identifying data of qualitative participants will be encrypted and stored in a separate password-protected server location to the transcripts. This document will be destroyed within 12 months of all publications and reports having been published.

Consent forms will be stored securely in locked filing cabinets in secure locations arranged by Research World International. These will be transferred to locked filing cabinets in Raising Voices' offices upon completion of each survey round. All data will be anonymised and will only be shared with study staff from Research World International, Raising Voices and LSHTM. They may also be shared with potential research degree students or collaborators interested in contributing to the analysis or conducting secondary analysis of anonymised data.

Ethics and safety

Ethical clearance will be sought from Institutional Review Boards at the London School of Hygiene and Tropical Medicine, Mildmay Uganda and the Uganda National Council for Science and Technology.

Approval to work in the study sites will be sought from the Chief Administrative Officer at the District level and the Local Council (LC) V Chairperson of the study District. Study information will be further shared with the Resident District Commissioner, LC3 and LC1 Chairpersons. Permission will

also be sought from local leaders at Parish- and Zone-level before any intervention implementation or data collection takes place. Communities will receive ongoing feedback throughout the study.

Individual written informed consent will be obtained for all community members participating in in-person surveys, IDIs, KIIs, FGDs and listener groups. In this process, an information sheet about the study will be read aloud to all participants by data collection staff. In cases where the participant is unable to read or write, an impartial witness must be present during the consent procedures and must print and sign their name, with the date, on the consent form on behalf of the potential participant. Participants who are unable to write will use thumbprints in place of signatures to sign the consent form.

Individual verbal informed consent will be obtained for all individuals participating in IDIs and KIIs conducted remotely by telephone. An information sheet about the study will be read aloud to all participants by the interviewer over the phone. The interviewer will discuss the information sheet with participants and seek verbal consent for their participation. If the participant gives verbal consent, the interviewer will attest to this by writing the name of the participant on a paper copy of the consent form and signing and dating their own name on the same form.

Of additional ethical concern is the sensitivity of the questions in the community survey. Although we will not ask directly about experiences of violence, the intervention content and the nature of the questions in the survey may evoke experiences that cause distress to respondents. Additional risks may be posed by the partner of a respondent finding out the nature of the interview. To minimise risk of harm to both respondents and interviewers, the study will adhere to the WHO recommendations for conducting research on domestic violence⁽¹⁹⁾. Actions include the careful wording of questions to ensure that they are non-judgmental, providing interviewers with intensive training on how to respond if someone discloses violence or requests assistance, providing all participants with information about potential sources of support, and ensuring that follow-up support can be made available if requested.

Enumerators will receive at least three weeks of training on the ethical and methodological issues surrounding the conduct of a survey relating to IPV, as well as ongoing support during the course of the survey. Interviewers will all be fluent in the local language (Lukonzo), and interview respondents of the same sex as themselves. Confidentiality will be maintained at all times.

Furthermore, when conducting IDIs and KIIs remotely, interviewers cannot be certain that participants are in a safe and private location. To enhance the safety of participants, interviewers will establish a “safe word” with the participant before the IDI or KII. This will be a word that the participant can use if, during the course of the interview, their safety is compromised. In this instance, the interview will be paused and postponed until a time when the participant can take part safely and privately.

UGANET and Raising Voices will create and update a referral list that includes formal and informal psycho-social-legal services for women experiencing VAW, including resources provided by UGANET (a helpline and shelter based in Kampala). This list is provided to all study participants irrespective of whether or not they have experienced VAW. If participants are taking part in remote IDIs or KIIs, they will be given the option to have the referral list shared with them by SMS. UGANET and Raising Voices will train research staff and programme facilitators on the use of the referral list. UGANET will have a dedicated staff member who will respond to new cases as they emerge. Programme activities will be monitored carefully for any signs of backlash.

Participants in study data collection who disclose any personal exposure to severe physical violence or sexual violence in the past year, or who report feeling unsafe and at risk of imminent violence, will be referred appropriately through UGANET established referral network including health, psychosocial, legal aid, shelter and other services.

Compensation

In line with the procedures of local ethics boards, as each session will take longer than 45 minutes, all participants in the study will be compensated with a token of appreciation for their time of the value of 10,000 Ugandan shillings (approximately 3 USD). All surveys participants will be offered a bar of a soap. FGD, IDI and KII participants will be offered 10,000 Ugandan shillings. In addition, FGD participants will be offered refreshments and, if they incur costs to travel to the site of the discussion, they will be reimbursed up to 10,000 Ugandan shillings.

As participation in listener groups is part of the implementation programme, we will not compensate participants in recorded listener groups.

For participants in IDIs and KIIs conducted remotely, compensation will be transferred to the participants in the form of mobile money. Participants will be reimbursed 11,000 Ugandan shillings to cover the mobile money withdrawal fee of 1,000 Ugandan shillings.

Protocol amendments

Several amendments have been made to the protocol since the study inception:

- Seven of the 22 villages in the original survey sampling frame were more remote than anticipated (3-4 hours walk from the next nearest village). For logistical purposes therefore, we decided to drop four of the less accessible villages from the sampling frame, while still retaining three of them in order to be able to estimate intervention reach to these more remote locations. The survey will now take place in a total of 18 villages.

Furthermore, an Ebola outbreak in the Western and Central regions of Uganda (September 2022 – January 2023) led to the following changes to the protocol:

- Cancellation of a planned midline survey of community members. Initially we planned three surveys (baseline, midline and endline), but this has now been changed to two surveys (baseline and endline).
- Larger sample size for the community-member survey at endline. Resources originally intended for the midline survey will be diverted towards the endline survey. We originally planned to survey 650 people at each of the three planned time-points. With cancellation of the midline, our endline target sample size has now been increased to 980.
- Change to remote data collection for first round of IDIs and KIIs (conducted approximately 19 weeks into Radio Booster programming). Originally these were intended to be conducted face-to-face, but will now be conducted over the telephone.
- Cancellation of middle round of FGDs with listener groups and CAs. Originally three rounds of FGDs were planned, but the round planned for 19 weeks into programming has now been cancelled.
- Listener group recordings (not originally planned) will now be instigated in lieu of the cancelled round of FGDs with listeners.

Dissemination strategy

